## 4. STUDY DESIGN

### 4.1. Overall Design

Study ALXN1210-COV-305 is a multicenter Phase 3, open-label, randomized, controlled study designed to evaluate the safety and efficacy of intravenous (IV) ravulizumab + BSC, compared with BSC alone, in patients with a confirmed diagnosis of SARS-CoV-2 infection, and a clinical presentation consistent with COVID-19 severe pneumonia, acute lung injury, or ARDS. Patients at least 18 years of age, weighing  $\geq 40$  kg, and admitted to a designated hospital facility for treatment will be screened for eligibility in this study. Accounting for a 10% nonevaluable rate, approximately 270 patients will be randomized in a 2:1 ratio (180 patients to receive ravulizumab + BSC, 90 patients to receive BSC alone).

Patients randomized to ravulizumab + BSC will receive a weight-based dose of ravulizumab on Day 1 (Table s1). On Day 5 and Day 10, doses of 600 mg or 900 mg ravulizumab will be administered (according to weight category) and on Day 15 patients will receive 900 mg ravulizumab. Patients in both treatment groups will continue to receive medications, therapies, and interventions per standard hospital treatment protocols for the duration of the study.

The study consists of a Screening Period of up to 3 days, a Primary Evaluation Period of 4 weeks, a final assessment at Day 29, and a Follow-up Period of 8 weeks. The 2 follow-up visits will be conducted 4 weeks apart as a telephone call if the patient is discharged from the hospital or an in-person visit if the patient is still hospitalized. The total duration of each patient’s participation is anticipated to be approximately 3 months (Figure 1).

Screening and the Day 1 visits can occur on the same day if the patient has met all inclusion and no exclusion criteria.

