#### Type of Patient and Disease Characteristics

2. Confirmed diagnosis of SARS-CoV-2 infection (eg, via polymerase chain reaction [PCR] and/or antibody test) presenting as severe COVID-19 requiring hospitalization.
3. Severe pneumonia, acute lung injury, or ARDS confirmed by computed tomography (CT) or X-ray at Screening or within the 3 days prior to Screening, as part of the patient's routine clinical care.
4. Respiratory distress requiring mechanical ventilation, which can be either invasive (requiring endotracheal intubation) or noninvasive (with continuous positive airway pressure [CPAP] or bilevel positive airway pressure [BiPAP]).

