6.2. Per Protocol Set (PPS)

The PPS is a subset of the ITT population without any important protocol deviations that could impact efficacy analyses. The PPS will include all patients who:

- Have no important protocol deviations or key inclusion/exclusion criteria deviations that might potentially affect efficacy,
- Are randomized to the ravulizumab + BSC group and receive 100% of the required treatment doses while they were in the treatment period in the ICU.

Important protocol deviation and key inclusion/exclusion criteria that will result in excluding patients from the PPS are discussed in [Section 7.1.2](#).

For ITT patients in the study who either die or are discharged from the ICU prior to Day 29, the compliance calculation for the per protocol set will include only the time period from the day of first dose to the day of death or ICU discharge.

The PPS will be determined prior to database lock and will be used in a sensitivity analysis of the primary and secondary efficacy endpoints.

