7.1.2. Protocol Deviations

Protocol deviations will be summarized in a tabular format and listing.

For the purposes of defining the PPS, important protocol deviations are:

- Not meeting all of the key inclusion/exclusion criteria.

Key inclusion criteria are:

- Confirmed diagnosis of SARS-CoV-2 infection (eg, via polymerase chain reaction [PCR] and/or antibody test) presenting as severe COVID-19 requiring hospitalization.
- Severe pneumonia, acute lung injury, or ARDS confirmed by computed tomography or x-ray at Screening or within the 3 days prior to Screening, as part of the patient's routine clinical care.
- Respiratory distress requiring mechanical ventilation, which can be either invasive (requiring endotracheal intubation) or noninvasive (with continuous positive airway pressure [CPAP] or bilevel positive airway pressure [BiPAP]).

Key exclusion criteria are:

- Patient is not expected to survive for more than 24 hours.
- Patient is on invasive mechanical ventilation with intubation for more than 48 hours prior to Screening.
- Severe pre-existing cardiac disease (ie, New York Heart Association Class 3 or Class 4, acute coronary syndrome or persistent ventricular tachyarrhythmias).
- Patients who took less than 100% of the required treatment doses while alive and in the ICU.

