7.1.3.2. Disease Characteristics

The following disease characteristics will be summarized:

- Number (percentage) of patients with a positive SARS-CoV-2 test
- Number (percentage) of patients hospitalized
- Number of days from onset of signs and symptoms to hospitalization and to Day 1
- Number of days from hospitalization to Day 1
- Number (percentage) of patients in the ICU
- Number of days from first ICU date to Day 1
- Oxygen saturation level (SpO₂), PaO₂ from arterial blood gas, amount of supplemental oxygen (FiO₂) received, SpO₂/FiO₂ and PaO₂/FiO₂ at baseline
- Number (percentage) of patients on respiratory support and method of support on Day 1
- SOFA score at baseline
- Number (percentage) patients by smoking status

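### The Per Protocol Set counts ravulizumab doses only while the patient is in the ICU, so a living ward patient given one, two or three of four scheduled doses is rated 100% compliant, and compliance is undefined for a patient never in the ICU

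*SAP*

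**What the plan says.** SAP 6.2 admits to the PPS ravulizumab patients who "receive 100% of the required treatment doses while they were in the treatment period in the ICU". For patients who die or leave the ICU before Day 29, the compliance calculation "will include only the time period from the day of first dose to the day of death or ICU discharge". SAP 7.1.2 repeats the rule as a deviation that removes a patient: "Patients who took less than 100% of the required treatment doses while alive and in the ICU".

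The regimen in Protocol 4.1 and Table 5 carries no such condition. "Patients randomized to ravulizumab + BSC will receive a weight-based dose of ravulizumab on Day 1", further doses follow on Days 5 and 10, and "on Day 15 patients will receive 900 mg ravulizumab". Protocol 6.6 rules out extra doses and says nothing about the ICU.

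Entry (Protocol 5.1) requires hospitalisation and mechanical ventilation, which may be CPAP or BiPAP. ICU admission is not a criterion. SAP 7.1.3.2 treats ICU status as something to be tabulated at baseline: "Number (percentage) of patients in the ICU".

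The protocol's own PPS definition (Section 9.3) has no dose or ICU rule. SAP 4.1, which lists departures from the protocol and says that the SAP prevails, does not mention this one.

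**The concern.** A per-protocol analysis is meant to show the comparison in patients treated according to the regimen. This rule measures adherence over a shorter period than the regimen covers, and that period ends when the patient improves enough to leave the ICU. Later missed doses are then ignored, while one missed dose in a patient still in the ICU leads to exclusion.

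Duration of ICU stay is also the second-ranked secondary endpoint. The number of doses a ravulizumab patient must have received to count as compliant therefore depends on an outcome of the trial. BSC patients have no dose requirement, so this dependence exists in one arm only.

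The PPS is the sensitivity population for the primary endpoint and for every secondary endpoint. A reader who takes it as the set of fully treated patients would be misled about what it contains.

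**Working it through.** The plan states no figure for PPS compliance, so there is none to reproduce. The check is a dose count.

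**Inputs.** Scheduled days 1, 5, 10 and 15, and the mg per dose by weight band (Protocol Table 5). Window and 100% requirement (SAP 6.2 and 7.1.2).

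**Formulas.**
- SAP score = doses received in the ICU window ÷ doses due in that window.
- Schedule score = doses received ÷ 4.
- Share of mg = mg received ÷ total mg. The totals are 2400 + 600 + 600 + 900 = 4500 (40 to <60 kg), 2700 + 3 × 900 = 5400 (60 to <100 kg) and 3000 + 3 × 900 = 5700 (≥100 kg).

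**Case 1: in the ICU from Day 1, every dose given until ICU discharge, none afterwards, alive and still in hospital.**

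| ICU discharge, example day | SAP score | Schedule score | Share of mg (40 to <60 / 60 to <100 / ≥100 kg) |
|---|---|---|---|
| Day 3 | 1/1 = 100% | 1/4 = 25% | 2400/4500 = 53.3%; 2700/5400 = 50.0%; 3000/5700 = 52.6% |
| Day 7 | 2/2 = 100% | 2/4 = 50% | 3000/4500 = 66.7%; 3600/5400 = 66.7%; 3900/5700 = 68.4% |
| Day 12 | 3/3 = 100% | 3/4 = 75% | 3600/4500 = 80.0%; 4500/5400 = 83.3%; 4800/5700 = 84.2% |
| Day 20 | 4/4 = 100% | 4/4 = 100% | 100% in each band |

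All four patients are rated identically.

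**Case 2: never in the ICU.** No dose falls due in the ICU, so the SAP score is 0/0 however many doses were given. The deviation in 7.1.2 is not triggered, the requirement in 6.2 cannot be evaluated, and the SAP does not say how to classify the patient. A related gap is that SAP 9.4.5.2 sets the time from first ICU entry to Day 1 to zero when it is negative. It thus allows for ICU entry after Day 1, in which case the Day 1 dose lies outside the ICU period.

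**Case 3: in the ICU on Day 1 and undosed.** The score is 0/1 = 0%, and the patient is excluded.

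**Can a bias be computed?** Let S be Day 29 survival in the ravulizumab arm, f the share of that arm removed for missed doses and s survival among those removed. PPS survival is (S − f·s)/(1 − f), so the shift is f(S − s)/(1 − f). Its sign depends on whether s is below or above S. The documents give neither f nor s, nor any distribution of ICU stay or share of patients never in the ICU. In addition, patients excluded for a dose missed in the ICU would also be excluded under any rule that counts those doses, so their removal does not measure the effect of the ICU wording.

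**The case against.** The best defence is that ending the window at ICU discharge avoids penalising recovery. After hospital discharge, follow-up is by telephone (Schedule of Activities footnote 3; Protocol 8.4.10), yet the patient remains alive and on study. A denominator of all doses due while alive and on study would remove patients who recovered and went home before Day 15, again in one arm only, and could bias the set the other way. This stands, and it limits the remedy. It does not justify a cut at ICU discharge, because a patient on a ward is still in hospital. Ending the window at death is reasonable, since no later dose can be given.

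Three stronger readings are tempting and are not supported.
- A reader might infer that patients given no drug count as fully dosed. For those who die or leave the ICU the window opens at the first dose, so it presupposes one; an undosed patient in the ICU on Day 1 fails; an undosed patient never in the ICU has an undefined score, not 100%.
- A reader might infer that the set is tilted toward ravulizumab. That needs f and s, which the documents do not give. Some one-arm dose selection is unavoidable when drug plus BSC is compared with BSC alone.
- Read literally, the second inclusion bullet admits only ravulizumab patients. The set supports comparisons between arms, and BSC patients have no doses to miss, so this is a drafting slip and not an intended exclusion.

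Two further points count in the plan's favour. SAP 7.1.1 already tabulates reasons for exclusion from analysis sets, and 7.3.1 summarises exposure, so under-dosing would be partly visible. The number of patients affected is unknown, and the design rationale in Protocol 4.2 has ICU patients in mind.

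**Conclusion.** The concern holds as a mismatch between the SAP's compliance rule and the protocol's regimen. Patients with 1, 2 or 3 of 4 scheduled doses can be rated 100% compliant, and the rule gives no answer for a patient never in the ICU. These results follow from the text alone, on the assumption that doses due after ICU discharge were missed.

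The consequence is confined to the PPS sensitivity analyses. The ITT primary test, its type I error, the sample size and the secondary testing order do not use this set. How many patients would be misclassified, and whether the PPS estimate would move up or down, cannot be determined from the documents. The rule is still worth correcting before the PPS is fixed at database lock, because this set backs up the primary and all secondary endpoints and its denominator depends on one of them.

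**What to change.** 1. In SAP 6.2 and 7.1.2, replace the ICU condition. Count every Table 5 dose scheduled while the patient was alive and in hospital, in the ICU or not. Start from Day 1 as SAP Section 7 defines it, which for an undosed patient is the later of randomisation and the Day 1 visit.
2. Reconcile the protocol's four-dose regimen with its telephone contact after hospital discharge. Let the handling of doses due after hospital discharge follow the reconciled text. This review takes no view on which dosing rule is right.
3. Split the second inclusion bullet in 6.2 by arm, so that BSC patients enter on eligibility and other important deviations alone.
4. Report the number excluded for missed doses and their Day 29 survival, so that any one-sided selection can be seen.

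The cost is a change of SAP wording and one derivation from dose dates that the CRF already records (Protocol 6.4). The downside is that the PPS may be somewhat smaller.

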6.3. Safety Set (SS)

The SS consists of all randomized patients who receive at least 1 dose of ravulizumab for patients randomized to ravulizumab + BSC or who are randomized to BSC alone. The SS will be used for the analysis of safety data.

Patients who have signed informed consent but are not randomized (or treated for ravulizumab + BSC group) in the study are not included in the SS. However, if these patients report SAEs after the signing of informed consent, these events will be summarized separately in listings, as appropriate.

6.4. Other Sets

6.4.1. Pharmacokinetic/Pharmacodynamic (PK/PD) Set

The PK/PD analyses will be performed on the PK/PD Set. This population includes patients in the ITT population with at least one post-dose PK or PD result.

7. STATISTICAL ANALYSIS

This study is a multicenter Phase 3, open-label, randomized, controlled trial designed to evaluate the safety and efficacy of IV ravulizumab + BSC, compared with BSC alone in patients with a confirmed diagnosis of SARS-CoV-2 infection, and a clinical presentation consistent with COVID-19 severe pneumonia, acute lung injury, or ARDS. The primary endpoint is survival (based on all-cause mortality) at Day 29.

An interim analysis for efficacy and futility is planned when approximately 50% of patients have completed Day 29. If the stopping criteria are met, the study may be terminated early for efficacy or futility depending on which stopping boundary is crossed. The early stopping boundaries for efficacy and futility (non-binding) will be constructed using an α -spending function as Lan-DeMets (O'Brien-Fleming) and a β -spending function as Gamma(-4), respectively.

Provided the study is not stopped early for efficacy or futility, the final primary analysis will be conducted when all patients have completed the Primary Evaluation Period, which is Day 29 (or early termination [ET]). This analysis will include all efficacy, safety, and available PK/PD/immunogenicity study data for regulatory submission purposes. This analysis will not be considered an interim analysis. A final analysis will be conducted when all participants have completed the study follow-up visits (or ET).

Day 1 will be defined as the date of the first infusion of ravulizumab for patients randomized and dosed with ravulizumab and as the later of the date of randomization or the date of Day 1 visit for patients randomized but not dosed with ravulizumab.

For this SAP, the randomization stratification factor refers to two strata based on endotracheal intubation status on Day 1: intubated or not intubated.

Summary statistics will be computed and displayed by treatment group and visit, where applicable. Descriptive statistics for continuous variables will include the number of patients, mean, standard deviation, median, minimum, and maximum. For categorical variables, frequencies, and percentages will be presented. Graphical displays will be provided as appropriate. Statistical analyses, other than for the primary analysis, will be performed based on a 2-sided Type I error of 5%.

Analyses will be performed using the Statistical Analysis Software (SAS®) Version 9.4 or higher.

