### 1.3. Schedule of Activities

**Table 1: Schedule of Activities**

Period	Screening Period	Primary Evaluation Period							Follow-up Period 	
		D1 	D5 	D10 	D15 	D22	D29/ Discharge 	Early Termination 	D60	D90
Study Day (D)	D -3 to D -1									
Study Window (days)	NA	NA	±1	±1	±1	±1	±1		±7	
Eligibility										
Informed consent	X									
Inclusion/exclusion	X									
Medical history 	X									
Demographics	X									
Study Administrative										
Confirmation of vaccination or appropriate antibiotic prophylaxis against N. meningitidis 	X								X	
Screening Laboratory Tests										
Confirmed positive SARS-CoV-2 test	X									
Chest CT or X-ray 	X									
Pregnancy test 	X						X	X		
Randomization										
Randomized to study drug + BSC or BSC alone		X								
Administration of Study Drug										
Ravulizumab 		X	X	X	X					
Efficacy Assessments										
Survival status										X
Mechanical ventilation status	X									
Hospitalization status										
Intensive care unit status										
Dialysis status										
FiO 2 , SpO 2 , PaO 2 										
Sequential Organ Failure Assessment score	X	X	X	X	X	X	X	X	X	
Safety Assessments										
Electrocardiogram	X						X	X		
Complete physical examination 	X						X	X		
Abbreviated physical examination 		X	X	X	X	X				
Glasgow Coma Scale	X	X	X	X	X	X	X	X		

Period	Screening Period	Primary Evaluation Period							Follow-up Period 	
		D1 	D5 	D10 	D15 	D22	D29/ Discharge 	Early Termination 	D60	D90
Study Day (D)	D -3 to D -1									
Study Window (days)	NA	NA	±1	±1	±1	±1	±1			±7
Body weight	X	X	X	X	X					
Vital sign measurements (predose) 	X	X	X	X	X	X	X	X		
Adverse event review and evaluation	X	<<monitor continuously>>								X
Review safety card 		X 					X 	X 		X 
Safety Laboratory Tests (Predose)										
Clinical chemistry	X	X	X	X	X	X	X	X		
Hematology	X	X	X	X	X	X	X	X		
Coagulation panel and D-dimer	X	X	X	X	X	X	X	X		
Urinalysis	X	X	X	X	X	X	X	X		
Direct Coombs test	X									

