### 9.4. Statistical Analyses

The primary analysis will be conducted when all patients have completed the Primary Evaluation Period. This analysis will include all efficacy, safety, and available PK/PD/immunogenicity study data for regulatory submission purposes and will be the final analysis of the Primary Evaluation Period.

Summary statistics will be presented by treatment group and by visit, where applicable. Descriptive statistics for continuous variables will minimally include the number of patients, mean, standard deviation, median, minimum, and maximum. For categorical variables, frequencies and percentages will be presented. Graphical displays will be provided as appropriate. All statistical analyses will be performed based on a 2-sided Type I error of 5%, unless otherwise noted.

Baseline is defined as the last available assessment on or before Day 1 for all patients. Day 1 will be defined as the date of the first infusion of ravulizumab for patients randomized and dosed with ravulizumab and as the date of randomization for patients randomized but not dosed with ravulizumab.

Analyses will be performed using SAS® software Version 9.4 or higher.

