4.1. Changes from Analyses Specified in the Protocol

The protocol states that the number of days free of mechanical ventilation at Day 29 will be compared between treatment groups using an analysis of covariance (ANCOVA), adjusting for age, and randomization stratification factor, *among survivors*. This has been clarified in [Section 7.2.2.1](#) of this SAP to be the number of days alive and free of mechanical ventilation; this represents a composite strategy for handling the intercurrent event of death.

The same modification applies to the duration of ICU stay at Day 29 *among survivors*, as well duration of hospitalization at Day 29 *among survivors*. These have been clarified in [Sections 7.2.2.2](#), [7.2.2.5](#), [9.4.5.2](#) and [9.4.5.3](#) of this SAP to be the number of days alive and not in the ICU and the number of days alive and not hospitalized, again representing a composite strategy for handling the intercurrent event of death.

Additional changes from the protocol are items 1, 2, and 4 given below in [Section 4.2](#) of this SAP. The analyses as specified in this SAP over-ride the protocol.

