4.2. Changes from Analyses Specified in the Previous Version of the SAP

1. The definition of Day 1 has been updated for patients randomized but not dosed with ravulizumab as the later of the date of randomization or the date of the Day 1 visit. This is to allow time for Day 1 assessments to occur on the following calendar day, but within 24 hours of randomization, for patients in the ICU, and to better align with the definition of Day 1 for patients randomized and dosed with ravulizumab (the date of the first infusion of ravulizumab).
2. Missing data sensitivity analyses for the primary endpoint have been added to [Section 7.2.1.1](#) as per feedback from health authorities and will include imputing any missing data assuming death, assuming survival, and performing a tipping point analysis.
3. For the sensitivity analyses of the primary endpoint using a 3-level categorical outcome and a logistic regression model, clarified in [Section 7.2.1.1](#) that the missing data for these analyses will be imputed as for the primary analysis using a multiple imputation approach assuming the data are missing at random (MAR) and using a logistic regression model with covariates for treatment group, the randomization stratification factor, age, sex and presence of a pre-existing condition at baseline.
4. In [Section 7.2.2.1](#), clarified that the number of days free of mechanical ventilation at Day 29 will be summarized by treatment group for all patients and by mortality and added a tipping point sensitivity analysis. These changes also apply to [Sections 7.2.2.2](#) and [7.2.2.5](#) for the durations of ICU stay and hospitalization.
5. In [Sections 7.2.2.3](#) and [7.2.2.4](#), added that for patients who die, remaining values up to Day 29 will be imputed as the worst possible value, representing a composite strategy for handling the intercurrent event of death.
6. For the exploratory endpoint of progression to renal failure, explained in [Section 7.2.3.1](#) that deaths will be assumed to be failures (a composite strategy for handling the intercurrent event of death) and that other missing data will be handled as described for the primary analysis of the primary endpoint.

The SAS code in [Appendix 9.5.2](#) has been updated to align with specified analysis methods as described in this SAP. Additional administrative changes have been made for accuracy, clarity and consistency.

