9.5. Additional details on Statistical Methods

9.5.1. Time to Death, Censoring Time, and Calculations

For the primary analysis, only deaths up to Day 29 will be considered, where time to death \leq 29 days.

For the KM sensitivity analysis of the primary endpoint, a censoring indicator will be equal to 1 if the patient did not die (was censored), and 0 if the patient died on or before 29 days.

For patients who die during the Primary Analysis Period, the time to event (in days) is defined as:

$$\text{Time to Death} = (\text{Date of Death} - \text{Date of Day 1} + 1)$$

For patients who do not die during the Primary Analysis Period, the censoring time (in days) is defined as:

$$\text{Censoring Time} = \min(29 \text{ days}, \text{time on study})$$

where time on study is Disposition Date – Date of Day 1 +1 for patients who have left the study before 29 days or Data Cutoff Date (when the last patient has the Day 29 visit) – Date of Day 1 + 1.

For the secondary endpoint of survival at Day 60 and Day 90, the following will be used:

For patients who die during the Analysis Period, the time to event (in days) is defined as:

$$\text{Time to Death} = (\text{Date of Death} - \text{Date of Day 1} + 1)$$

For patients who do not die during the Analysis Period, the censoring time (in days) is defined as:

$$\text{Censoring Time} = (\text{EOAP Date} - \text{Date of Day 1} + 1)$$

where End of Analysis Period (EOAP) Date is the minimum non-missing value of the following dates: the Data Cutoff Date (when the last patient has the Day 29 visit) and the Final Disposition Date for patients who have left the study before the data cutoff date. Deaths observed after the EOAP date will not be included in the analysis.

These derivations will be repeated with the data cutoff date defined as when the last patient has completed the study.

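### Day 29 survival is counted from Day 1, a date that depends on dosing received, rather than from randomisation

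*SAP*

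**What the plan says.** **Time zero.** SAP 9.5.1 says "For the primary analysis, only deaths up to Day 29 will be considered, where time to death" is at most 29 days, and computes time to death as date of death minus date of Day 1, plus 1. The window therefore closes 28 days after Day 1.

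**Day 1.** SAP Section 7, repeated in 9.4.2, gives two rules. For dosed patients, "Day 1 will be defined as the date of the first infusion of ravulizumab for patients randomized and dosed with ravulizumab". For everyone else, Day 1 is set "as the later of the date of randomization or the date of Day 1 visit for patients randomized but not dosed with ravulizumab". The second rule covers the whole BSC-alone arm and any ravulizumab-arm patient who is never infused.

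**Protocol.** Protocol 9.4 defines Day 1 for undosed patients "as the date of randomization for patients randomized but not dosed with ravulizumab". SAP 4.2, item 1, changes this openly. Its reason is "This is to allow time for Day 1 assessments to occur on the following calendar day, but within 24 hours of randomization", together with closer agreement with the infusion-based rule. SAP 4.1 adds "The analyses as specified in this SAP over-ride the protocol".

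**Planned timing.** Table 1 of the protocol puts the row "Randomized to study drug + BSC or BSC alone" and the first ravulizumab dose in the same D1 column, with no visit window for D1. Exclusion criterion 5 and Section 6.5.1 also place randomisation on Day 1.

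**Stratum.** SAP Section 7 says "the randomization stratification factor refers to two strata based on endotracheal intubation status on Day 1". Protocol 6.3 stratifies randomisation on the same item, and the SAS notes in SAP 9.5.2.1 identify the variable as the randomisation stratification factor.

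**Population.** The primary analysis is intention-to-treat: every randomised patient, in the assigned group (SAP 6.1).

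**The concern.** An intention-to-treat comparison of survival normally starts the clock at randomisation, because that is the last moment at which the groups are comparable by design. Here the clock starts at a date that can fall later, under a rule that depends on whether the patient was dosed. If that date falls g days after randomisation, the patient is at risk for 28 + g days from randomisation before being counted as a survivor. If g differs on average between the arms, the arms are compared over spans of different length.

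The study is open-label (Protocol 6.3), so infusion and Day 1 visit dates are set by staff who know the allocation. Neither document limits the time from randomisation to infusion. The 24-hour figure applies to undosed patients and appears only as a reason in SAP 4.2; the operative definitions in SAP 7 and 9.4.2 leave it out. The sensitivity analyses in SAP 7.2.1.1 and 7.2.1.5 do not include one anchored at randomisation.

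At stake is a small possible bias in the primary risk difference. The same start date feeds the days-alive endpoints in SAP 9.4.5.

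**Working it through.** **Inputs.** Survival 60% (BSC alone) and 80% (ravulizumab + BSC), 81 and 162 patients, 1-sided type I error 0.025, pooled variance (Protocol 9.2, SAP 9.3). The window runs to 28 days after Day 1 (SAP 9.5.1). The gap g is not given in the documents, so 1 to 3 days is an assumption used to show scale.

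**Step 1: the plan's own figure.** Fixed-design power = Φ[(d − 1.96·SE0)/SE1].
- Pooled survival = (81×0.60 + 162×0.80)/243 = 0.7333.
- SE0 = √[0.7333×0.2667×(1/81 + 1/162)] = 0.0602.
- SE1 = √[0.60×0.40/81 + 0.80×0.20/162] = 0.0629.
- Power = Φ[(0.20 − 0.1179)/0.0629] = 90.4%, which agrees with the stated 90%. Also 243/0.90 = 270.

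The interim look is left out of the comparisons below. Day 1 timing is not an input to the design, so the fix leaves 243, 270 and the type I error unchanged.

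**Step 2: one extra day.** With constant hazard, h = −ln(S)/28, and the survival lost in one more day is S(1 − e^−h).
- S = 0.60: h = 0.01824, loss 1.08 points.
- S = 0.80: h = 0.00797, loss 0.64 points.

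If the hazard near Day 29 is half the average, these halve to about 0.5 and 0.3 points. If only a quarter of an arm shifts by a day, they fall to about 0.27 and 0.16 points.

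**Step 3: a whole arm shifts and the other does not.**

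| Later window | Days | Difference (points) | Fixed-design power |
|---|---|---|---|
| Neither | 0 | 20.0 | 90.4% |
| Ravulizumab | 1 | 19.4 | 88.3% |
| Ravulizumab | 2 | 18.7 | 86.0% |
| Ravulizumab | 3 | 18.1 | 83.4% |
| BSC alone | 1 | 21.1 | 92.9% |

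**Step 4: no true effect, 60% survival in both arms.** A one-day shift of one whole arm gives a spurious difference of 1.08 points, with a standard error of about 0.067.
- BSC later: 1-sided type I error = 1 − Φ(1.96 − 0.0108/0.0668) = 0.036.
- Ravulizumab later: 1 − Φ(1.96 + 0.0108/0.0669) = 0.017.

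**Step 5: both arms shift by one day.** Under the planned effect, survival becomes 58.9% and 79.4%, a difference of 20.4 points, so the net change is about 0.4. With no true effect the shifts cancel exactly.

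**Step 6: deaths before infusion.** A ravulizumab-arm patient who dies before infusion is undosed, so Day 1 falls under the other rule. Time to death is at most 29 days and the death counts.

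**The case against.** The strongest reply is that the plan intends no gap. Table 1 puts randomisation and first dose on one visit, and the eligibility text places randomisation on Day 1. A delay would then be a matter of conduct rather than design. The SAP also saw the asymmetry, moved the undosed rule closer to the dosed one, gave its reason and declared precedence over the protocol. This stands as far as it goes: Day 1 is planned to be the randomisation date and often will be. But the SAP changed the rule because some Day 1 assessments may slip to the next calendar day, so it does foresee a gap for undosed patients, and no limit is set for dosed ones. Moving a second start date later narrows the mismatch on average; a common randomisation date removes it.

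Four stronger readings are tempting, and the documents do not support them.
- **That Day 1 is defined by arm.** The split is by dosing received. Undosed ravulizumab-arm patients share the BSC rule.
- **That the bias runs against the drug.** This needs infusion to lag randomisation by more than the undosed patients' Day 1 does. With same-day infusion and a next-day BSC visit, the sign reverses.
- **That the primary test uses a post-randomisation stratum.** The Day 1 wording allows the question, but the variable is labelled the randomisation stratification factor, and randomisation is stratified on it, so its value must be known at allocation.
- **That early deaths are lost.** Step 6 shows that they are not.

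**Conclusion.** The point holds as a minor one. The primary survival window starts at Day 1 rather than at randomisation, and its start depends on dosing received. The end of the window can therefore differ between patients, and on average between arms, measured from randomisation.

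The effect is probably small. It is about 0.6 to 1.1 points of survival per day if one whole arm shifts and the other does not, assuming constant hazard at 60% and 80% survival. It is less if only some patients shift or the late hazard is lower, and it largely cancels if both arms shift equally. The figures in Steps 3 and 4 for a single shifted arm are upper limits for the stated number of days, not forecasts. The documents do not report the actual gap, so neither the size nor the direction can be fixed from them. No sample size, boundary or type I error in the plan needs to change.

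The stratum wording is an ambiguity that one sentence would settle, not an error.

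**What to change.** - In SAP 9.5.1, count survival over 28 days from the randomisation date for all intention-to-treat patients. Do the same in SAP 9.4.5 for the days-alive endpoints, where daily status is available from randomisation. Keep Day 1 for dosing and visit scheduling.
- Report the randomisation-to-Day 1 interval by arm.
- As a clarification, state in SAP Section 7 that the intubation stratum in every stratified analysis is the value recorded at randomisation.

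If the sponsor prefers to keep Day 1 as time zero, a randomisation-anchored sensitivity analysis of the primary endpoint is the minimum.

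The cost is SAP wording and a change of one date variable in the programs. Randomisation dates should be held for every patient. Because Day 1 cannot precede randomisation under either rule, a cut-off 28 days after randomisation always falls on or before Day 29 as now counted, so no extra follow-up is needed. The change should be made before comparative results are seen.
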